20. Department of Immunology, School of Medicine, Tehran University of Medical Sciences, Tehran, Iran.	[name] (Iran) Investigator
21. Department of Rheumatology, Peking Union Medical College Hospital, Beijing, China	[name] (China) Investigator
22. Internal Medicine Department, Ibn Sina University Hospital, Rabat, Morocco.	[name] (Moroc) Investigator

BACKGROUND

Behçet's syndrome (BS) is a multisystem inflammatory disease of unknown etiology, characterized by strong genetic background, distinctive geographic distribution, and wide variability in clinical presentation [1]. Disease activity related to BS as well as chronic exposure to medications may lead to the development and accrual of irreversible organ damage resulting in impairment of quality of life, disability, and increased mortality [2]. For these reasons, organ damage was included in the OMERACT outcome core set for BS [3].

The Behçet's syndrome Overall Damage Index (BODI) is a recently developed tool to identify and measure organ damage in BS [2]. The BODI is grounded in a solid evidence-based and consensus-based methodology, and its preliminary validation on a multicenter cohort of Southern European patients showed highly promising performance in terms of comprehensiveness, specificity, reliability, sensitivity to change, and feasibility [2].

Nevertheless, a prospective validation with a wider and ethnically heterogeneous cohort of BS patients is needed to generally evaluate the impact of those BODI items seldom recorded or absent in the preliminary validation cohort and to weigh the damage items depending on their relevance for predicting major outcomes.

OBJECTIVES

General objectives

The general objectives of the PROBE study are to further test the comprehensiveness of the BODI (content validity) in a wide and ethnically heterogeneous cohort of BS patients, and investigate how damage assessed by the BODI correlates with other major long-term disease outcomes (criterion validity), with the ultimate goal of drafting a weighing system for each BODI item.

Specific Objectives

1. To test the comprehensiveness of the instrument in a wide and ethnically heterogeneous cohort of BS patients, evaluating the prevalence of those BODI items seldom recorded or absent in the preliminary validation cohort
2. To describe possible differences in the entity and type of damage accrual in BS patients from different geographical areas.
3. To identify the factors independently associated with damage development and accrual.

4. To investigate the association between the results of the baseline BODI measurement (BODI ≥ 1 , BODI score, and BODI ranking) and the 5-years mortality rate.
5. To investigate the association between the results of the baseline BODI measurement (BODI ≥ 1 , BODI score, and BODI ranking) and the 5-years hospitalization rate.
6. To weigh each item of damage depending on their relevance in predicting mortality.

METHODS

Study design

PROBE is an observational multicenter cohort study, consisting of a cross-sectional and a 5-years prospective phase, designed to target the major study objectives, such as testing the content and criterion validity of the BODI and drafting a weighing system for each BODI items.

During the study, patients will undergo a routine clinical assessment, as scheduled in their follow-up program. No further clinical, laboratory or instrumental investigations are required in addition to those provided according to good clinical practice. Treatment prescription will be evaluated by each investigator independently from the study and according to the international and local guidelines and the good clinical practice.

Patients

The study population will consist of consecutive BS patients diagnosed according to the ICBG or ISG classification criteria [4,5] recruited in Centers with expertise for BS.

Inclusion criteria:

- Diagnosis of BS according to ICBG or ISG criteria;

Exclusion criteria:

- subjects unable or unwilling to make themselves available for the duration of the study and/or are unwilling to follow interval visits.

Any effort should be addressed by investigators to minimize the rate of lost to follow-up and guarantee the completeness of the database.

Data collection

Data will be collected at the time of recruitment (baseline, T0) and then annually (± 1 month) for 5 years. Overall, 6 visits are planned to be recorded (T0, T1, T2, T3, T4, T5). Details on the data required at each visit are reported in table 1.

A query management system (QMS) will manually track data queries so they can be adequately individualized and resolved. QMS substantially minimizes and even eliminates the risk of invalid data being unnoticed. Collected data will be checked annually and data queries (e.g., data issue) will be forwarded to Investigators. Data queries will only be resolved in the following ways:

- by correcting the error, in other words entering a new value that is valid;
- by marking the data in conflict as correct.

Table 1. Data collection at each scheduled visit

Months	T0	T1	T2	T3	T4	T5
	Baseline	12 (± 1)	24 (± 1)	36 (± 1)	48 (± 1)	60 (± 1)
Demographics	P					
Comorbidities	P					
Cumulative disease manifestations	P					
Active manifestations between visits		P	P	P	P	P
BD current activity form (BDCAF)	P	P	P	P	P	P
BODI score	P	P	P	P	P	P
Physician global assessment (PGA)	P	P	P	P	P	P
Patient's global assessment (PtGA)	P	P	P	P	P	P
Patient's damage assessment (PtDA)	P	P	P	P	P	P
Ongoing treatment	P	P	P	P	P	P
N of relapses (between visits)	Last 5 yrs	P	P	P	P	P
N of hospitalizations (between visits)	Last 5 yrs	P	P	P	P	P
Death		P	P	P	P	P

Variables

Details on the variables that are requested to be recorded are reported below:

- **Demographics:**

- Gender (male/female)
- Date of birth
- Date of onset:
 - a) first disease manifestation including oral aphthosis;
 - b) first disease manifestation excluding oral aphthosis
- Date of diagnosis
- Date of enrolment
- Smoking:
 - never smoker,
 - current smoker,
 - past smoker
- Country of origin
- Country of residence
- Ethnicity:
 - Caucasian;
 - Asian;
 - Hispanic;
 - Afro-American;
 - Arab;
 - Other (please specify)
- Education level:
 - Illiterate
 - Primary school
 - Secondary School
 - College/University
- Comorbidities:
 - Fibromyalgia
 - Blood hypertension

- Dyslipidemia
- Obesity (BMI>30)
- Chronic Kidney disease
- Diabetes (diagnosed before onset of BS)
- Other (please specify)

○ **Cumulative clinical manifestations:** any disease manifestation occurred from the disease onset to the enrolment visit (even no longer present at the enrolment visit). The following disease manifestations have to be recorded:

- Oral aphthosis (yes/no)
- Genital aphthosis (yes/no)
- Skin lesions (yes/no, if yes specify which type)
- Ocular (yes/no, if yes specify which type)
- Vascular (yes/no, if yes specify which type)
- Neurologic (yes/no, if yes specify which type)
- Musculoskeletal (yes/no, if yes specify which type)
- Gastrointestinal yes/no, (if yes specify which type)
- Pathergy test (yes/no)
- Others yes/no, (if yes specify which type)

○ **Active clinical manifestations between visits:** manifestations that are present at the time of the visit or have occurred since last visit. The following disease manifestations have to be recorded:

- Oral aphthosis (yes/no)
- Genital aphthosis (yes/no)
- Skin lesions (yes/no, if yes specify which type)
- Ocular (yes/no, if yes specify which type)
- Vascular (yes/no, if yes specify which type)
- Neurologic (yes/no, if yes specify which type)
- Musculoskeletal (yes/no, if yes specify which type)
- Gastrointestinal yes/no, (if yes specify which type)
- Pathergy test (yes/no)
- Others yes/no, (if yes specify which type)

- **Behçet's disease current activity form (BDCAF) score:** BDCAF is a disease activity assessment tool for BS. It depends on an accurate evaluation of clinical features present during the month before the date of assessment. The presence/absence of 9 somatic symptoms from a list may be recorded, together with eye involvement, nervous system involvement, major vessel involvement, as well as the clinician's overall perception of disease activity. The transformed index score on an interval scale will be used for analysis in the present study. [6]
- **Behçet's syndrome overall damage index (BODI):** It is a tool recently developed to identify and measure organ damage in BS. BODI consists of 4 overarching principles and 34 items with 12 subitems, categorized into 9 organ/system domains: mucocutaneous, musculoskeletal, ocular, vascular, cardiovascular, neuropsychiatric, gastrointestinal, reproductive system, and miscellaneous. Each item and subitem scores 1 point. The total score ranges from 0 to 46 [2]. In order to score the BODI, each investigator will be provided with a user manual and a video tutorial (<https://vimeo.com/264992929>).
- **Physician's global assessment of disease activity (PGA):** It will be assessed through a single question ("How active is the patient's BS?") on an anchored 10-cm visual analogic scale (0.5-cm graded), where 0 corresponded to "no disease activity" and 10 to "the highest disease activity." [7]
- **Patient's global assessment of disease activity (PtGA):** It will be assessed through a single question ("How active was your BS during the last week?") on an anchored 10-cm visual analogic (0.5-cm graded), where 0 corresponded to "no disease activity" and 10 to "the highest disease activity." [7]
- **Patient's damage assessment (PtDA):** It will be assessed through a single question ("How much irreversible (non-healing) damage have you developed since the diagnosis of BS?") on an anchored 10-cm visual analogic (0.5-cm graded), where 0 corresponded to "no damage" and 10 to "the highest amount of damage".
- **Ongoing treatment:** medications that are ongoing at the time of each visit will be classified as:
 - Colchicine (yes/no)

- Glucocorticoids (yes/no, if yes specify the current dosage in mg/day of prednisone or equivalents)
 - Conventional immunosuppressant (yes/no, if yes which agent; i.e., azathioprine, cyclosporine, cyclophosphamide, thalidomide, methotrexate, sulphasalazine; others)
 - Apremilast (yes/no)
 - Biologic immunosuppressant (yes/no, if yes which agent; i.e. anti-TNFalpha agents)
 - Other (yes/no, if yes specify)
- **Number of relapses.** Relapse is defined as the onset of a new BS manifestation or recurrence/worsening of a pre-existing clinical manifestation resulting in significant treatment modifications. Significant treatment modifications will be defined as the starting or increasing dosage of corticosteroids, colchicine, apremilast, conventional or biologic immunosuppressant. For each relapse, the clinical manifestation inducing the treatment modification will be recorded.
- **Number of hospitalizations.** Hospitalization will be defined as any admission to the hospital (duration at least one day including emergency room) for any reason both related to BS (i.e. treatment, management of complications, diagnosis of new manifestations, etc.) and unrelated to BS (i.e. surgery, cardiovascular disease, malignancy, etc.). Primary reasons and numbers of days of hospitalization will be recorded.
- **Death** (yes/no, date of death, cause of death). In this regard, it is of extreme importance to make every possible effort to ensure that patients resulting lost to follow-up have not deceased.

Statistical analysis

Descriptive statistics will be performed to report on the prevalence and amount of damage, as assessed by the BODI. In the whole study cohort and different geographical sub-groups, the damage will be described as:

- prevalence of any damage (BODI ≥ 1);
- prevalence of any damage in the different BODI domains;
- mean (SD) or median (IQR) BODI score;

- ranking of the BODI score will be developed, using a multistate model, depending on the distribution of damage in the whole population.

Univariate and multivariate regression models will be implemented to investigate the significant difference between ethnic/geographic groups in terms of prevalence and amount of damage accrual. Similarly, univariate and multivariate regression models will be implemented to investigate independent factors associated with the development or accrual of damage, as assessed by the BODI.

Multivariate Cox proportional hazards regression models will be created to assess the effect of damage (BODI score, BODI ≥ 1 , BODI ranking) on subsequent risk of death with adjustment for covariates, including gender, age, disease duration at enrollment, history of major organ involvement, disease activity at enrolment, comorbidities (onset before BS diagnosis). Results will be presented as hazard ratios with their corresponding 95% confidence intervals. Statistical significance will be defined as a P-value <0.05 . Finally, adjusted survival estimates obtained from these Cox regression models were plotted as survival curves.

Sample size

According to the results of previous studies, 95% overall 5-year survival is expected [8]. Assuming 99% and 95% of survival rate in BS patients with and without BODI damage, respectively, and assuming 50% prevalence of damage (BODI ≥ 1) in the study cohort, we estimated a required sample size of at least 801 BS patients (alpha type I error = 0.05; beta type II error 0.20) to identify damage as a predictor of mortality. Under the assumption of 25%maximum attrition (5% every year), the sample size will be increased to 1040 patients.

STUDY TIMELINE

March 2021 – June 2021: Investigators involvement and Ethic Approval (if locally required)

April 2021 – December 2021: Enrollment window

January 2022 – December 2026: Prospective follow-up window

Publication plan:

- **End of 2022 :** Publication of Cross-sectional results (*content validity*)
- **End of 2025:** Publication of mid-term results (factors associated to damage accrual)

- **End of 2028:** publication of prospective results (*construct validity*)

PUBLICATION RULES

Baseline data will be published in a peer-reviewed scientific journal within 1 year from the end of recruitment. The full results of the prospective validation will be published in a peer-reviewed scientific journal following the completion of the 5-year study. Partial or preliminary results can be published beforehand.

The main publication is the responsibility of the Principal Investigator. Authorship in the main publications, as well as in ancillary papers, will be offered to all Investigators who achieve the minimum target of 30 patients with complete clinical data after 5 years of follow-up. All the other Investigators not reaching these criteria will be included in the collaborator's list according to the table below. Any exception could be evaluated, depending on the number of enrolled patients with complete data, by taking into account the national epidemiological distribution of BS. Investigators will be listed in authorship according to the number (from highest to lowest) of enrolled patients.

Number of patients	Investigator	Local co-investigator
>100	Author	Author
30-100	Author	Collaborator
<30	Collaborator	Collaborator

A list of ancillary publications will be discussed; the study proponent will be granted to access the entire data-set and will lead the ancillary publication. Authorship of ancillary papers will be the same as the main publications.

ETHIC AND REGULATORY ISSUES

Ethical Committee Approval

Ethical Committee Approval will be obtained by the Proposing and Coordinating Centre (Rheumatology Unit, AOU of Cagliari, Italy) and in the other Research Centres in accordance with the policy of the Institutions and local legislation for this kind of study. Any future change to the protocol or informed consent needed over the study must be approved by Ethical Committee.

Data Collection

Demographic, clinical and therapeutic data will be collected during the enrolment visit and annually for 5 years during the routinary follow-up visits for each patient, by reviewing medical records and clinical files. No further clinical, laboratory or instrumental investigations will be performed in addition to those provide by the good clinical practice. No experimental drugs will be administrated. Any possible drug administration will be evaluated independently to the study and according to the good clinical practice and the observational nature of the study.

Data entry and security

The collected data from each Research Centre will be anonymously recorded in an electronic spreadsheet. Anonymous data form each Research Centre will be subsequently entered into a single password-protected database managed and guarded by the Coordinating Research Centre (Rheumatology Unit, AOU of Cagliari, Italy). To guarantee anonymity, an alphanumeric code will be attributed to each patient by the recruiting physician. The correspondence between the alphanumeric code and the patient's identity will be reported in a sperate document, accessible only to the recruiting physician. Access to patient final database will be restricted to the Chief Investigator and Collaborators above.

Informed consent

The recruiting physician must inform patients on every aspect of the study, including his right to withdraw at any time. The decision of participating to the study must be voluntary. In accordance with the policy of the Institutions and local legislation of each Research Centre for this kind of study, a signed informed consent will be obtained at the enrolment and a copy of will be provided to the recruited patient also. The informed consent will be signed by the recruiting physician also.

Study withdrawal

Every recruited patient can withdrawal from the study at any time for any reason. If his data yet entered in the database and not published, they will be removed.

Data publication and privacy

Following completion of the study, the full results will be published in a peer-reviewed scientific journal. The data anonymity will be guaranteed in accordance with the personal data protect laws.

Insurance cover

For the purely observational nature of the study, no further insurance coverage should be requested in addition to that provided for the standard clinical practice by each Research Centre.

Funding

No specific funding is provided for the study

REFERENCES

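### Objective 1 measures how often listed BODI items occur, which does not show whether the BODI is comprehensive, and no field itemises damage the BODI leaves out

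*Protocol*

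**What the plan says.** The General objectives of the Protocol state that the study will "further test the comprehensiveness of the BODI (content validity) in a wide and ethnically heterogeneous cohort of BS patients". Specific Objective 1 then says how this will be done: by "evaluating the prevalence of those BODI items seldom recorded or absent in the preliminary validation cohort".

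Under Variables, the instrument is described as a closed list: "BODI consists of 4 overarching principles and 34 items with 12 subitems, categorized into 9 organ/system domains". Each item and subitem scores one point, and the total runs from 0 to 46. One of the nine domains is called miscellaneous. The items themselves are not printed in the protocol.

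One other variable is dedicated to damage. The PtDA asks the patient "How much irreversible (non-healing) damage have you developed since the diagnosis of BS" on a 0 to 10 visual scale, and Table 1 schedules it at all six visits.

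Open text is also collected. Manifestations carry the entry "Others yes/no, (if yes specify which type", cumulative at T0 and since the last visit at T1 to T5. Comorbidities carry "Other (please specify", at T0 only. The primary reason for each hospitalization and the cause of death are recorded too.

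The Statistical analysis section describes damage through the BODI: any damage, "prevalence of any damage in the different BODI domains", the score and its ranking.

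**The concern.** An instrument is comprehensive if it covers the damage that patients actually have. The way to test this is to look for damage it does not cover. Objective 1 looks instead at how often the items already on the list are scored. That shows whether each listed item is relevant or possibly redundant, which is a useful but different property.

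The difference matters in this study. The Background says that the preliminary validation was done in Southern European patients and that BS varies widely in presentation. The wider cohort is meant to test the instrument elsewhere. On the stated measure, a BODI that omitted a type of damage seen mainly in a newly included region would give the same kind of result as a complete one. Content validity is also the subject of the first planned publication (end of 2022), so a claim of comprehensiveness would be the study's first public conclusion.

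**Working it through.** The plan gives no figure for this objective, so there is none to reproduce. The check is what each recorded variable can say about damage outside the BODI, followed by what the prevalence exercise can and cannot show.

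**Step 1. What each variable can show (Table 1 and Variables)**

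| Variable | Visits | Asks about irreversible damage? | Names the lesion? |
|---|---|---|---|
| BODI | T0 to T5 | Yes | Only if it is listed |
| PtDA | T0 to T5 | Yes, since diagnosis | No |
| Manifestations, typed and other | T0 to T5 | No; includes resolved ones | Yes |
| Comorbidities, other | T0 | No | Yes |
| Hospitalization reason | T0 to T5 (the last 5 years at T0) | No | Possibly, if admitted |
| Cause of death | T1 to T5 | No | Possibly, if died |

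No row both asks about irreversible damage and names a lesion that the BODI does not list. The Background says that damage also arises from long exposure to medication. Such damage is not a disease manifestation. After T0, unlisted treatment damage in a patient who is neither admitted nor dies has no field meant for it.

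**Step 2. What the prevalence of listed items shows**

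For a listed item with true prevalence p, the chance of seeing it at least once in N patients is 1 − (1 − p)^N. With p = 0.3% (an illustrative value):
- N = 801: 1 − 0.997^801 = 0.91
- N = 1040: 1 − 0.997^1040 = 0.96

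If a listed item is never seen, the one-sided 95% upper bound on its prevalence is 1 − 0.05^(1/N):
- N = 801: 0.37%
- N = 1040: 0.29%

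The cohort is therefore large enough to settle whether rare listed items occur. An unlisted lesion does not enter either formula, so a larger N does not help.

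**Step 3. What a dedicated field would show**

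The proportion of patients with unlisted damage is unknown. Assuming 1%, 3% or 5%:
- of 1040: 0.01 × 1040 = 10, 0.03 × 1040 = 31, 0.05 × 1040 = 52
- of 801: 8, 24 and 40

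If no case were reported among 1040, the upper bound would be 1 − 0.05^(1/1040) = 0.29%, provided that investigators recognise and report every case. If they recognised only half (an assumption), it would be about 0.29% / 0.5 = 0.58%. By area the statement is weaker: a single site at the 30-patient authorship target gives 1 − 0.05^(1/30) = 9.5%.

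**Step 4. How far the PtDA can stand in**

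A patient with BODI = 0 and PtDA > 0 may have unlisted damage. The comparison cannot name the lesion, and it leaves out damage that arose before diagnosis. It also cannot see unlisted damage in a patient who has any listed damage. The Sample size section assumes 50% with BODI ≥ 1, so the comparison would be silent for about 0.5 × 1040 = 520 patients.

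**The case against.** The strongest reply is that the protocol is consistent about its purpose. The Background says that the wider cohort is needed to evaluate items that were rare or absent before, and it reports that comprehensiveness already looked promising in the preliminary validation. On this view the fault is mainly the label. That is partly right: the planned work is coherent as a study of item occurrence. But the protocol equates comprehensiveness with content validity and sets out to test it further, and item occurrence does not do so.

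Second, damage outside the BODI is not wholly unrecorded. A reader might infer that no variable captures it, or that the whole data set is blind to missing content. The documents do not support that. The PtDA measures irreversible damage independently of the BODI at six visits, and an unusual lesion could be written in several open-text fields. What stands is narrower: these are indirect signals, and none identifies a lesion as damage.

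Third, the items and the scoring manual are not shown, so the breadth of the miscellaneous domain cannot be judged, nor whether any particular regional lesion would go unscored. That stands. The point is that the plan cannot tell, and no specific omission is alleged.

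Fourth, a comparison of the PtDA or the free text with the BODI could be specified in an SAP. That also stands, and its absence here is not held against the protocol. The objective's definition and the data fields are fixed in the protocol, and an SAP cannot recover lesions that were never itemised.

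Finally, a reader might infer that unlisted damage contaminates the reference group of the mortality analysis. It does not. Objective 4 asks whether the BODI measurement predicts death, and BODI = 0 is the right reference for that question.

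**Conclusion.** The point holds as stated in the heading. Objective 1's measure gives no information on missing content at any sample size, and the data set has only indirect routes to it. Followed as written, the study can support a statement that listed items do or do not occur in a wider population. It cannot support a statement that the BODI is comprehensive.

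The size cannot be fixed from the documents, because the frequency of unlisted damage is unknown. Over an assumed 1% to 5%, it concerns 10 to 52 of 1040 patients. The conclusion rests on reading the BODI as a fixed list, which the 34 + 12 = 46 one-point entries and the 0 to 46 range support. It is confined to the content-validity objective and its publication. The change is worth making, but the rest of the study does not depend on it.

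**What to change.** 1. Add one field beside the BODI at each visit: irreversible damage judged due to BS or its treatment and not covered by any BODI item (yes/no; if yes, specify).
2. Reword Objective 1 so that comprehensiveness is the proportion of patients with such damage, overall and by geographical area, each with a confidence interval. Report the prevalence of previously rare or absent items separately, as item relevance.
3. For visits where the field was not collected, limit the conclusion to item occurrence. Use the cross-tabulation of BODI = 0 against PtDA > 0 as a supportive check only.

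The cost is one spreadsheet entry per visit, a protocol change for ethics approval and some free text to code centrally. No extra investigation is needed, so the observational design is unchanged. The remaining weakness is that the result depends on investigators recognising unlisted damage, so the field needs a short instruction in the BODI user manual.

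### The sample-size survival assumptions are reversed (99% with damage, 95% without), and in either order they imply 97% overall survival, not the 95% expected in the same paragraph

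*Protocol*

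**What the plan says.** Everything needed is in the Sample size section of the protocol (under Methods) and in the Background.

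- The paragraph begins with an expectation taken from the literature: "According to the results of previous studies, 95% overall 5-year survival is expected".
- The next sentence gives the planning rates: "Assuming 99% and 95% of survival rate in BS patients with and without BODI damage, respectively, and assuming 50% prevalence of damage", together with "alpha type I error = 0.05; beta type II error 0.20".
- From these it derives at least 801 patients, and the stated purpose is "to identify damage as a predictor of mortality".
- The Background describes the expected direction of effect: disease activity and chronic medication exposure may lead to "irreversible organ damage resulting in impairment of quality of life, disability, and increased mortality".

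**The concern.** There are two separate faults in the inputs.

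1. **Direction.** Because the sentence pairs the rates with the groups in order, 99% belongs to patients with damage and 95% to those without. Damage is then protective, which is the opposite of the Background and of the purpose of the calculation.
2. **Consistency.** Two equal groups with 99% and 95% survival cannot have 95% survival overall. Reversing the labels does not cure this.

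This paragraph is the protocol's only sample-size justification. It supports specific objective 4, the association of baseline BODI with 5-year mortality. The number of deaths, more than the number of patients, limits what the planned covariate-adjusted Cox model can estimate, so a plan that leaves open whether mortality is 3% or 5% leaves that point unsettled.

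**Working it through.** **Inputs (all from the Sample size section):** overall survival 95%; group survival 99% and 95%; prevalence of damage 50%; alpha 0.05; power 80%; N = 801. The protocol does not say whether the test is one- or two-sided, nor which formula was used. I assume a two-sided test unless stated otherwise.

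**1. The plan's own 801.** The pooled two-proportion formula for deaths of 1% and 5%, equal groups, is

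n per group = [1.960·√(2·0.03·0.97) + 0.842·√(0.01·0.99 + 0.05·0.95)]² / 0.04² = (0.4728 + 0.2016)² / 0.0016 ≈ 284.3, rounded up to 285, so **570 in total**.

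Other standard choices:

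| Method | Total N |
|---|---|
| Pooled, two-sided, continuity-corrected | 666 |
| Pooled, one-sided (continuity-corrected) | 448 (544) |
| Unpooled, two-sided | 564 |
| Arcsine, two-sided | 500 |
| Schoenfeld, 12 events / 0.03 | 400 |
| Freedman, 18 events / 0.03 | 600 |

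None gives 801, so the figure cannot be used to work back to the rates that were intended.

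**2. Direction.** Under proportional hazards the hazard ratio for damage is ln(S with damage) / ln(S without damage).

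- As written: ln(0.99) / ln(0.95) = 0.01005 / 0.05129 = **0.20**.
- Labels reversed: ln(0.95) / ln(0.99) = **5.10**.

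At 50% prevalence the calculation is symmetric in the labels, so the swap changes neither N, nor the size of the log hazard ratio, nor total deaths.

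**3. Overall survival.** 0.5 × 99% + 0.5 × 95% = **97%**, in either order. With these two rates, 95% overall would require every patient to be in the 95% group.

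**4. Deaths among 801 patients** (the protocol gives no figure).

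- At 97% overall: 801 × 0.03 = 24.0, made up of 400.5 × 0.05 = 20.0 and 400.5 × 0.01 = 4.0.
- At 95% overall: 801 × 0.05 = 40.1.

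**5. Power at N = 801** (400.5 per group, same two-proportion formula, unadjusted). Only the first row uses the protocol's rates. The others are illustrative pairs that average 95%.

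| Survival without / with damage | Overall | Hazard ratio | N for 80% power | Power at 801 |
|---|---|---|---|---|
| 99 / 95 | 97% | 5.1 | 570 | 91% |
| 99 / 91 | 95% | 9.4 | 232 | above 99% |
| 98 / 92 | 95% | 4.1 | 412 | 97% |
| 97.5 / 92.5 | 95% | 3.1 | 596 | 90% |
| 97 / 93 | 95% | 2.4 | 930 | 74% |

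Solving for exactly 80% power at 801 with 95% overall gives a gap of 4.3 points (97.15% versus 92.85%, hazard ratio 2.6). Power is below 80% only if the true gap is narrower than that.

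**The case against.** The strongest reply is that nothing practical follows. The reversal is plainly a slip of wording: the Background and the stated purpose leave the intended direction in no doubt, the swap has no numerical effect, and the Cox analysis does not depend on the order of the labels. The 95% overall figure could be read as literature context, because the sentence that produces 801 lists the group rates, the prevalence and the error rates, but not that figure. If the hazard ratio of 5.1 is kept and overall survival set to 95% (about 98.3% versus 91.7%), power at 801 is about 99%. Shortfalls appear only for gaps that the protocol never states, and all these powers are unadjusted, whereas the planned model adjusts for covariates.

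Much of this stands. The reversal taken alone is an erratum, and no shortage of patients has been shown. It does not remove the second fault. The 95% opens the sample-size paragraph as what is expected, it is the only figure there with a source, and the text gives no reason for departing from it. Since 801 does not follow from the listed inputs by the standard formulas tried, a reader cannot use it to confirm that the group rates were the real basis.

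**Conclusion.** The paragraph is wrong as written on both counts. It states the planning effect in the wrong direction (hazard ratio 0.20 where 5.1 must have been meant). It also combines 99% and 95% survival, 50% prevalence and 95% overall survival, which cannot all be true; the first three give 97%. The second error amounts to about 24 against about 40 deaths among 801 patients.

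The consequence for power is limited and uncertain in direction. On the stated group rates 801 patients give about 91%. If 95% overall is the intended basis, the answer runs from about 74% (97% versus 93%) to above 99% (99% versus 91%), depending on a gap the protocol does not state. These figures assume a two-sided 5% test, equal groups, complete follow-up of 801 patients and no covariate adjustment. They do not show that 801 is too small. The point should be fixed; it does not call the study's size into question.

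**What to change.** In the Sample size section:

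1. Reverse the labels, so that 99% applies to patients without damage and 95% to those with damage.
2. Make the rates agree. Either replace the 95% overall expectation with the implied 97% and say why it differs from the cited figure, or choose group rates that average 95% at 50% prevalence.
3. State the hazard ratio and the number of deaths that these inputs imply.
4. Restate the power of the planned cohort under the corrected inputs. Naming the formula and the sidedness of the test would let a reader check it.

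The cost is one reworded paragraph and one recalculation. No extra patients, visits or data are needed, and no change in enrolment is asked for.
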